Evaluation of Mailers Promoting Mammogram Screening
(NCT04555902)

Study Protocol with Statistical Analysis Plan

June 11, 2021

Study Protocol

Purpose

The purpose of this study is to evaluate, prospectively, the potential impact of different mailer conditions (standard content including a free gift, content designed with behavior science, content designed with behavior science including a free gift) on mammogram screening.

Introduction

Mammogram screening for women, starting at age 50, can significantly reduce the risk of complications due to breast cancer. As part of an existing outreach campaign, the health system mails a postcard and small gift (pink socks) to women on the month of their 50th and 64th birthdays to promote annual mammogram screening.

The researchers are evaluating two new versions of the mailers against a standard mailer to see which version leads to greater uptake in mammograms. The new mailers had content that applied behavioral nudge theory - specifically, loss frames and fear appeals - to encourage taking action. One of the two new versions did not include the small gift, to test whether its inclusion or exclusion has any effect on mammogram screening.

Methods

Sample

Female Geisinger Health Plan members turning age 50 and 64 in that month were included in the study. Although the intervention began in October, women with birthdays as early as June 2020 were included. These additional participants were included because the mailer program was paused from June to October 2020 due to the COVID-19 pandemic; the October mailing was meant to contact all the eligible women who were not contacted since June.

Experimental conditions

All participants received a two-sided, 9x6 postcard that had a picture and attention-grabbing slogan in the front. The back of the postcard included a brief, persuasive message, with a toll-free number that could be used for scheduling a mammogram. Participants were randomly assigned to receive one of the three versions of mailers detailed below.

Standard Version with Socks (V1): The picture in front showed a woman posing against a pink background. The slogan in front said, “It’s time to think pink” and the back of the postcard mentioned that staying healthy benefited the recipient and their loved ones. It encouraged recipients to get their annual mammogram and show they are “part of the fight against breast cancer” by putting on some cute pink socks. This postcard and a pair of pink socks were sent together in a larger envelope.

Enhanced Version without Socks (V2): The picture in front showed two women with pink- and grey-colored clothing jogging together. The slogan in front said, “To do: Lower my risk of breast cancer.” The back of the postcard framed an annual mammogram as the best way to find and beat breast cancer, with late detection leading to more costs, less effective treatments, and lower chances of recovery. Like the standard version, it mentioned that staying healthy benefited the recipient and their loved ones. This version was not accompanied by socks and was not sent in an envelope.

Enhanced Version with Socks (V3): This postcard was identical to V2, with the exception of an additional message at end, which asked recipients to accept the socks as a small gift and reminder to take care of their health. This postcard and a pair of pink socks were sent together in a larger envelope.

Outcome measures

The primary outcome measure was mammogram completion (yes/no) 6 months from the intervention date.

The secondary outcome measures were mammogram completion at 12 months (yes/no), primary care provider (PCP) visits (count) at 6 and 12 months, Obstetrician-Gynecologist (OB-GYN) visits (count) at 6 and 12 months, breast cancer diagnosis (lab notes) at 6 and 12 months, and emergency department visits (count) at 6 and 12 months.

Exploratory outcome measures were mammogram completion, primary care provider visits, breast cancer diagnosis, and emergency department visits in 2019.

The preregistered plan was to randomly assign participants to different groups through April 2021 (6 months from the start of the intervention; April mailers were sent on April 6, 2021). However, data have not yet been viewed or analyzed as of the uploading of this document. Therefore, random assignment continued past April 2021 and will continue until results inform a decision regarding which version should be sent to all participants. Data until April 2021 will be pulled and examined for the primary analysis. Data past April 2021 may be examined in exploratory analyses.

Statistical Analysis Plan

As of the writing of this plan, all mailers have been sent and the data have not yet been examined.

Primary Research Question: Which mailer version leads to more mammograms?

H1a: Compared to V1, V2 will lead to more mammograms at 6 months.

H1b: Compared to V1, V3 will lead to more mammograms at 6 months.

The researchers do not have a hypothesis on whether sending enhanced versions with or without socks (V2 and V3) would lead to more mammograms.

For these analyses, a logistic regression will be used, using the following model: Outcome ~ Condition. In the model, V2 and V3 will be entered as predictors with V1 as the reference group. For all tests, two-tailed p-values < 0.05 were used to determine statistical significance.

Secondary Research Question 1: Which mailer version leads to greater improvements in health-related outcomes?

H2a: Compared to V1, V2 will lead to more PCP visits, OB-GYN visits (both as proxies for engagement with the health system), and less emergency department visits (less acute issues) at 6 months.

H2b: Compared to V1, V3 will lead to more PCP visits, OB-GYN visits (both as proxies for engagement with the health system), and less emergency department visits (less acute issues) at 6 months.

The researchers do not have a hypothesis on whether sending enhanced versions with or without socks (V2 and V3) would lead to better health-related outcomes.

For these outcomes, regression models with a log-link function and negative binomial distribution will be used (accounting for positively skewed count or count-related data). If the negative binomial models fail to converge or fit appropriately, a Poisson distribution or another model appropriate for the outcome data will be used instead.

The following basic model will be used for the above analyses: Outcome ~ Condition. For each outcome, V2 and V3 will be entered as predictors with V1 as the reference group. For all tests, two-tailed p-values < 0.05 were used to determine statistical significance.

Secondary Research Question 2: Which mailer version leads to more mammograms and greater improvements in health-related outcomes in the long term (12 months)?

H3a: Compared to V1, V2 will lead to more mammograms, PCP visits, OB-GYN visits (both as proxies for engagement with the health system), and less emergency department visits (less acute issues) at 12 months.

H3b: Compared to V1, V3 will lead to more mammograms, PCP visits, OB-GYN visits (both as proxies for engagement with the health system), and less emergency department visits (less acute issues) at 12 months.

The researchers do not have a hypothesis on whether sending enhanced versions with or without socks (V2 and V3) would lead to better health-related outcomes.

For the mammograms, a logistic regression will be used. For the PCP visits, OB-GYN visits, and emergency department visits, regression models with a log-link function and negative binomial distribution will be used (accounting for positively skewed count or count-related data). If the negative binomial models fail to converge or fit appropriately, a Poisson distribution or another model appropriate for the outcome data will be used instead.

The following basic model will be used for the above analyses: $\text{Outcome} \sim \text{Condition}$. For each outcome, V2 and V3 will be entered as predictors with V1 as the reference group. For all tests, two-tailed p-values < 0.05 were used to determine statistical significance.

Exploratory Research Question: Which mailer version leads to greater improvements in health-related outcomes over time?

H4a: Compared to V1, V2 will lead to a greater increase over time of PCP visits, OB-GYN visits (both as proxies for engagement with the health system), and decrease over time emergency department visits (less acute issues) in the 12 months after the intervention date compared to 12 months before the intervention date.

H4b: Compared to V1, V3 will lead to a greater increase over time of PCP visits, OB-GYN visits (both as proxies for engagement with the health system), and decrease over time emergency department visits (less acute issues) in the 12 months after the intervention date compared to 12 months before the intervention date.

The researchers do not have a hypothesis on whether sending enhanced versions with or without socks (V2 and V3) would lead to better health-related outcomes.

While the number of mammograms 12 months before the intervention was included as an outcome in the Clinical Trials record, this will no longer be analyzed, as having mammograms in this time period was part of the exclusion criteria. The preregistration of this outcome at this particular time period was done in error.

For the PCP visits, OB-GYN visits, and emergency department visits, mixed-effects regression models with a log-link function and negative binomial distribution will be used (accounting for positively skewed count or count-related data). If the negative binomial models fail to converge or fit appropriately, a Poisson distribution or another model appropriate for the outcome data will be used instead.

The following random intercepts model will be used for the above analyses: $\text{Outcome} \sim \text{Condition} + (1| \text{Participant})$. For each outcome, V2 and V3 will be entered as predictors with V1 as the reference group. For all tests, two-tailed p-values < 0.05 will be used to determine statistical significance.

Examination of Additional Outcomes

Only descriptive statistics will be reported for breast cancer diagnoses at 6 and 12 months. These will be used to illustrate how many people detected breast cancer due to the program and to estimate the costs to the hospital system.

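### The mammogram models pool two age cohorts and an October catch-up group without using age or mailing wave; adjusting for both and reporting by age is a cheap improvement, probably small in precision, and not a bias correction

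*Combined protocol and SAP*

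**What the plan says.** Sample (Study Protocol, Methods): "Female Geisinger Health Plan members turning age 50 and 64 in that month were included in the study". The same section adds: "Although the intervention began in October, women with birthdays as early as June 2020 were included". It explains that the programme had been paused and that "the October mailing was meant to contact all the eligible women who were not contacted since June".

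Allocation (Study Protocol, Experimental conditions): "Participants were randomly assigned to receive one of the three versions of mailers detailed below". No ratio, blocking or stratification is given.

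Analysis (Statistical Analysis Plan, Primary Research Question): "a logistic regression will be used, using the following model: Outcome ~ Condition. In the model, V2 and V3 will be entered as predictors". Secondary Research Question 2 uses the same condition-only form for mammograms at 12 months. Neither the protocol nor the SAP uses age cohort, mailing month or catch-up status as a covariate, stratification factor, subgroup or sensitivity analysis.

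Two further statements bear on how the groups may differ. The Introduction says "Mammogram screening for women, starting at age 50, can significantly reduce the risk of complications due to breast cancer". The Exploratory Research Question says of the 12 months before the intervention that "having mammograms in this time period was part of the exclusion criteria".

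The protocol says the results will inform the choice of a single version for everyone. The SAP says the data have not yet been examined.

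**The concern.** The two birthdays sit at different points of the screening range: one at its start, the other 14 years in (64 − 50). Completion rates, and possibly the response to a loss-framed card, could differ between them. Women with June to September birthdays were mailed one to four months after the birthday, whereas the routine programme mails in the birthday month.

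If age or wave predicts completion, leaving them out of the model gives up some power. More important for the decision, a single pooled odds ratio cannot show whether the preferred version works at both ages, although both ages would receive it. Within-age estimates added after the data are seen would be post hoc; added now, they are prespecified.

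**Working it through.** The documents give no sample size, power, effect size, completion rate, allocation ratio or age split, so there is no stated figure to reproduce. All rates and arm sizes below are assumptions used to size the point. Only the 0.05 two-sided level comes from the SAP.

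**1. Share of catch-up women.** Birthdays from June 2020 to April 2021 span 11 months. The October mailing covers June to October, which is 5 months; June to September, 4 months, were mailed late. With equal births per month, 5/11 = 45% of the primary sample is in the October mailing and 4/11 = 36% was mailed late.

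**2. Outcome variance explained by age and catch-up status.** Formula: between-stratum variance of risk ÷ p(1 − p), with equal age cohorts.
- 20% and 25% by age: 0.025² ÷ (0.225 × 0.775) = 0.4%.
- 15% and 30% by age: 0.075² ÷ (0.225 × 0.775) = 3.2%.
- 15% and 30%, catch-up women 5 points lower: (0.075² + 0.05² × 4/11 × 7/11) ÷ (0.2068 × 0.7932) = 3.8%. With 10 points lower: 5.2%.

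The equivalent gain in sample size is 1 ÷ (1 − share) − 1, so 0.4% to about 5%.

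**3. Power with and without a two-level term.** Assumed: 1,000 per arm, conditional OR 1.3, two equal strata. Power = Φ(|log OR| ÷ SE − 1.96). The unadjusted test uses the marginal OR and its SE; the adjusted test uses the conditional OR and the stratum-combined SE.

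| V1 rates | Power, unadjusted | Power, adjusted | Equivalent extra women (risk-difference scale) |
|---|---|---|---|
| 20% / 20% | 68.1% | 68.1% | 0% |
| 20% / 25% | 71.2% | 71.4% | 0.4% |
| 20% / 30% | 73.1% | 73.7% | 1.4% |
| 15% / 35% | 69.2% | 71.7% | 6.1% |
| 10% / 40% | 62.2% | 68.1% | 14.8% |

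The SE of the log-OR does not fall: at 20%/30% it goes from 0.1004 to 0.1011, and at 10%/40% from 0.1007 to 0.1079. The power gain comes from the larger conditional OR. On the risk-difference scale it comes from a smaller variance.

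**4. What pooling can hide.**
- Equal cohorts: 20% to 26% at one age (OR 1.41) and 30% to 27% at the other (OR 0.86) average to 25.0% and 26.5%. Pooled OR = (0.265/0.735) ÷ (0.25/0.75) = 1.08.
- Milder case: with 20% on V1 at both ages and ORs of 1.6 and 1.0, the pooled OR is 1.28.
- For that milder case a treatment-by-age test has power of 22%, 33%, 58% and 86% at 300, 500, 1,000 and 2,000 per arm. Estimates with intervals therefore say more than an interaction p-value.

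**5. Dependence on a constant allocation ratio.** Suppose 40% of V1 but 30% of V3 fell in a catch-up mailing with 20% completion, against 30% elsewhere, and no version had any effect. V1 would show 0.4 × 20% + 0.6 × 30% = 26% and V3 would show 0.3 × 20% + 0.7 × 30% = 27%: a false difference of 1 point (OR 1.05). Nothing in the documents suggests that this happened.

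**6. Would opposite signs by age mean anything?** With no effect at either age, the two estimates have opposite signs 50% of the time per contrast. With a common OR of 1.1 (V1 rates 15% and 30%, equal cohorts), they do so about 44%, 39% and 31% of the time at 500, 1,000 and 2,000 per arm.

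**The case against.** The strongest reply is that nothing in the planned test is wrong. A prespecified unadjusted comparison of randomised arms is legitimate, the programme sends one mailer to both birthdays, and the pooled average answers the question of which one to send. No hypothesis by age is stated, and the masking examples in step 4 are constructed. This stands, and it limits the point to an improvement.

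Four stronger readings are tempting, and the documents support none of them.
- **That the pooled result is biased.** It is not, provided the ratio was constant across mailings. The documents are silent on the ratio, which is a reason to state it and not evidence of a fault.
- **That precision is materially lost.** No rate by age or wave is given. The power gain is below 1 point when the rates differ by 10 points or less, and only a very strong age or wave effect brings it near 6 points.
- **That late-mailed women are specially selected for not having screened.** The exclusion looks back 12 months from the intervention, so the window ends at mailing for every woman, on time or late. Extra selection is arguable only at 50, where screening is said to start. Completion in the catch-up group could be lower, or higher through deferred demand; the documents support neither direction.
- **That opposite directions at 50 and 64 should lead to different mailers by age.** Step 6 shows how often that would happen by chance.

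What survives is that both variables are already held, using them costs almost nothing, and no planned analysis shows the effect in either age cohort.

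**Conclusion.** The point holds as a recommended improvement in efficiency and interpretation. The mammogram models ignore two baseline variables known before mailing, and the plan has no estimate by age although the chosen version will go to both ages. The likely precision gain is small: about 0.4% to 5% equivalent sample size under the plausible rates in step 2, and larger only if age or wave shifts completion by 20 points or more. These figures rest on assumed completion rates, equal cohorts and equal births per month. The validity of the unadjusted test rests on a constant allocation ratio, which should be confirmed.

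**What to change.** Before data are examined:

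1. State the allocation ratio, whether it was the same in every mailing, and whether randomisation was stratified.
2. For mammogram completion at 6 and 12 months, prespecify Outcome ~ Condition + AgeCohort (50/64) + MailingWave, with October split into on-time (October birthdays) and catch-up (June to September birthdays). Name the adjusted condition terms as the ones that test H1a and H1b.
3. Report standardised risk differences for V2 − V1 and V3 − V1 with 95% CIs, beside the conditional odds ratios and the unadjusted result.
4. Report both contrasts with 95% CIs within each age cohort, and once without the June to September birthdays. Label these as descriptive consistency checks, with no roll-out rule triggered by opposite signs.

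Cost: a few lines of SAP text and model code, since birth and mailing dates are needed to run the programme and should already be held. Downsides: the adjusted odds ratio is conditional and not directly comparable with the unadjusted one, its log-scale standard error can rise slightly, and the within-age intervals will be wider than the pooled ones.

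### The 6- and 12-month mammogram models omit pre-mailing screening history; a clearly defined 2019 covariate could add modest power at little cost

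*Combined protocol and SAP*

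**What the plan says.** The Outcome measures section states: "The primary outcome measure was mammogram completion (yes/no) 6 months from the intervention date". Under the Primary Research Question, H1a and H1b compare V2 and V3 with V1, and "a logistic regression will be used, using the following model: Outcome ~ Condition". Secondary Research Question 2 repeats this at 12 months: "For the mammograms, a logistic regression will be used", again with condition as the only predictor. The significance rule is "For all tests, two-tailed p-values < 0.05 were used to determine statistical significance".

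The Outcome measures section also says: "Exploratory outcome measures were mammogram completion, primary care provider visits, breast cancer diagnosis, and emergency department visits in 2019". Under the Exploratory Research Question the plan drops the registered count of mammograms in the 12 months before the intervention: "this will no longer be analyzed, as having mammograms in this time period was part of the exclusion criteria". It adds that registering that measure was an error. The plan does not say whether the 2019 entry and the withdrawn 12-month entry are the same measure. The exclusion is mentioned only there; the Sample section does not list it.

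**The concern.** Mammogram completion in 2019 precedes every mailing, so no mailer can change it. It cannot serve as an outcome of the trial. Its natural use is as a baseline covariate, since past screening is a plausible predictor of later screening. The plan lists it as an exploratory outcome and leaves it out of the two models where it could help.

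What is at stake is efficiency, not validity. The results are meant to inform the choice of mailer for all recipients. If the differences between postcards are small (an assumption; the plan states no expected effect), some extra power is worth having. Adjustment also corrects for chance imbalance between arms in the share of earlier screeners.

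**Working it through.** The plan states no sample size, power, event rate or effect size, so there is no figure to reproduce. The check has four steps.

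**1. Does a 2019 record still vary among eligible women?** Inputs from the documents: "women with birthdays as early as June 2020 were included"; the June to October birthdays share the October 2020 mailing; the primary data run to April 2021. Assumptions: equal cohort sizes, whole-month counting, and a look-back of exactly 12 months.

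| Mailing | Birthday cohorts | 2019 months inside the look-back | Cohort-months |
|---|---|---|---|
| October 2020 | 5 | 3 | 15 |
| November 2020 | 1 | 2 | 2 |
| December 2020 | 1 | 1 | 1 |
| January to April 2021 | 4 | 0 | 0 |

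The total is 18 of 11 × 12 = 132 cohort-months. So 18/132 = 14% of 2019 is forced to zero and 114/132 = 86% can vary. Read literally, calendar 2019 is not constant. Read as the 12 months before mailing, the covariate is 0 for every woman and the gain is exactly zero. Note that 86% of the months need not carry 86% of the predictive information.

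**2. Test of the arm effect in the logistic model.** "Participants were randomly assigned to receive one of the three versions of mailers detailed below"; no ratio is given, so equal allocation is assumed. Other assumptions: 1,000 women per arm, 30% completion under V1, conditional odds ratio 1.35 for each new mailer (log 0.300), 30% of women with the covariate, two-sided alpha 0.05. The efficiency ratio is (adjusted estimate/SE)² ÷ (unadjusted estimate/SE)², from the expected information.

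| Covariate odds ratio | Unadjusted log OR (SE) | Power | Adjusted log OR (SE) | Power | Efficiency ratio |
|---|---|---|---|---|---|
| 2 | 0.293 (0.0953) | 86.8% | 0.300 (0.0964) | 87.5% | 1.02 |
| 4 | 0.272 (0.0954) | 81.3% | 0.300 (0.1003) | 84.9% | 1.10 |
| 8 | 0.239 (0.0956) | 70.6% | 0.300 (0.1072) | 79.9% | 1.25 |

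The SE rises in every row. Power increases because the conditional log odds ratio is further from zero than the marginal one. Over 300 or 1,000 per arm, V1 rates of 15% or 30% and prevalences of 10%, 30% or 50%, the ratio is about 1.01 to 1.03 at odds ratio 2, 1.04 to 1.11 at 4, and 1.10 to 1.25 at 8.

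**3. Risk-difference scale.** Standardising over the covariate multiplies the variance by about 1 − φ², where φ is the correlation between covariate and outcome. For φ = 0.1, 0.2, 0.3 and 0.4 the variance falls by 1%, 4%, 9% and 16%. Interval width scales with the square root, so at φ = 0.4 it is √0.84 = 0.92 of the unadjusted width.

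**4. Sensitivity to the assumed rates.** With prevalence p and completion r1 (with a 2019 mammogram) or r0 (without), R² = p(1 − p)(r1 − r0)² / [r̄(1 − r̄)], and the gain in effective sample size is 1/(1 − R²) − 1.
- Cautious case: p = 10%, r1 = 35%, r0 = 20%, so r̄ = 0.215. R² = 0.09 × 0.15² / (0.215 × 0.785) = 0.012, a gain of about 1%.
- More favourable cases: 2019 prevalence of 20–30% at age 50 and 40–50% at age 64, r0 of 15–20%, r1 of 40–60%. The R² added on top of an age term was 0.042 to 0.160, a gain of about 4% to 1/0.84 − 1 = 19%. In 4,000 simulated trials per scenario, power at 1,000 per arm rose by between 1.0 point (65.4% to 66.4%) and 7.2 points (53.4% to 60.6%), with type I error of 4.7–5.6%. These runs compared age alone with age plus the 2019 record and had no category for women not enrolled in 2019, so they only approximate the model proposed below.

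**The case against.** The strongest objection is that the covariate may not exist in usable form. The plan withdraws the pre-mailing mammogram measure, and it appears to use 2019 and the 12 months before mailing loosely: primary care and emergency visits are listed for 2019 among the outcomes, but H4 analyses them over the 12 months before the intervention. This stands as a reason to define the covariate explicitly. It does not defeat the point, because a record confined to the part of 2019 before the look-back is not constant.

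Second, the association may be weak. The exclusion removes women who kept to an annual pattern, and the age-50 group was about 48 to 49 in 2019, below the starting age given in the Introduction. Women not enrolled in 2019 would dilute the gain further. This stands too, and is why the range starts near 1%.

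A reader might infer three stronger things that the documents do not support:
- That the planned comparison is biased or invalid. It is not; arms were randomised and the condition-only test is sound.
- That adjustment would tighten the interval for the log odds ratio. Step 2 shows its SE rises, and the estimand changes from a marginal to a conditional odds ratio.
- That a ready-made covariate is being passed over for nothing. The measure must first be defined and reconciled with the exclusion.

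**Conclusion.** The point holds as a modest, inexpensive improvement to a valid analysis. Both mammogram models are condition-only, and the plan names a pre-mailing record of the same behaviour without using it as a covariate. Adjusting for screening history before the exclusion window would add power and narrow the standardised risk-difference interval, to the extent that this history is prognostic.

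The size cannot be determined from the documents. Under assumed prevalence and association the gain in effective sample size runs from about 1% to 20–25%. It is nil if the 2019 measure means the 12 months before mailing. The 86% calendar figure rests on equal cohorts and a 12-month look-back; a longer exclusion window would leave less of 2019 to vary.

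**What to change.** 1. Reconcile the Outcome measures section with the Exploratory Research Question. Define the covariate as mammogram completion in calendar 2019 before the 12-month exclusion window: yes, no, or not observable because not a plan member. List it as a baseline covariate, not an exploratory outcome.
2. Before the data are viewed, prespecify Outcome ~ Condition + this covariate for H1 and for the H3 mammogram analysis, with V2 and V3 each tested against V1.
3. Report standardised completion rates per arm and the V2−V1 and V3−V1 risk differences with 95% intervals, since the adjusted odds ratio is conditional.
4. Keep Outcome ~ Condition as a sensitivity analysis.

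The cost is SAP wording and a few lines of code: one covariate definition, a category for missing membership and a standardisation step. No further women or mailings are needed. The plan states that the data have not been examined, so prespecification was still credible at its date.

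### The no-gift arm exists to test the gift's effect on mammograms, but no V3 versus V2 contrast, the only one that isolates the sock package, is planned

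*Combined protocol and SAP*

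**What the plan says.** The Introduction gives two aims. The first is "evaluating two new versions of the mailers against a standard mailer to see which version leads to greater uptake in mammograms". The second explains why one new version came without the gift: "to test whether its inclusion or exclusion has any effect on mammogram screening".

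Experimental conditions defines the three arms. For both V1 and V3, "This postcard and a pair of pink socks were sent together in a larger envelope". For V2, "This version was not accompanied by socks and was not sent in an envelope". Of V3 it says "This postcard was identical to V2, with the exception of an additional message at end".

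In the SAP the heading question is "Primary Research Question: Which mailer version leads to more mammograms". H1a compares V2 with V1 and H1b compares V3 with V1, at 6 months. On the remaining pair the SAP says only: "The researchers do not have a hypothesis on whether sending enhanced versions with or without socks (V2 and V3) would lead to more mammograms". The analysis is a logistic regression of outcome on condition: "In the model, V2 and V3 will be entered as predictors with V1 as the reference group". All tests are two-tailed at 0.05. Secondary Research Question 2 uses the same model and coding for 12-month mammogram completion.

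The end of the Methods says that random assignment will go on until the results guide the choice of one version for everyone.

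**The concern.** With V1 as reference, the model's two condition coefficients are V2 minus V1 and V3 minus V1. They serve the first aim. Neither serves the second, and nothing in the document commits to a V3 versus V2 contrast, a change of reference group, a set of pairwise tests, an omnibus test or an interval.

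Two things are at stake. A stated aim would go without a prespecified analysis. And the choice between V2 and V3, which is part of the rollout decision, would have no planned measure of uncertainty. Whether and how the comparison is reported could then be settled after the results are known.

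The point is limited to mammogram completion. The gift aim in the Introduction does not extend to visit counts.

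**Working it through.** **Step 1. What each contrast varies** (from Experimental conditions)

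| Contrast | Postcard content | Socks and envelope | Planned? |
|---|---|---|---|
| V2 − V1 | standard to enhanced | removed | yes (H1a) |
| V3 − V1 | standard to enhanced | present in both | yes (H1b) |
| V3 − V2 | enhanced in both, plus a closing line about the socks | added | no |

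V2 − V1 mixes content with the sock package. V3 − V1 has socks in both arms. Only V3 − V2 varies the package with the main content fixed.

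**Step 2. The contrast is available from the planned model**

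With coefficients b2 (V2 − V1) and b3 (V3 − V1), the V3 versus V2 odds ratio is exp(b3 − b2), with variance Var(b3) + Var(b2) − 2Cov(b2, b3). The model has three parameters for three arms, so this equals the two-arm result from counts: SE = √(1/a + 1/b + 1/c + 1/d), where a to d are completers and non-completers in the two arms.

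**Step 3. Can the planned tests stand in for it?**

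The documents give no sample size, allocation ratio or expected rates, so there is no figure of the plan's own to reproduce. All inputs from here on are assumptions.

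*Example A: 1,000 per arm, completions 400, 370 and 430 (V1, V2, V3).*

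- V2 − V1: OR = (370/630)/(400/600) = 0.88 (95% CI 0.74 to 1.05), p = 0.168.
- V3 − V1: OR = (430/570)/(400/600) = 1.13 (0.95 to 1.35), p = 0.173.
- V3 − V2: OR = (430/570)/(370/630) = 1.28. SE = √(1/370 + 1/630 + 1/430 + 1/570) = 0.0915. log OR = 0.250, z = 0.250/0.0915 = 2.74, 95% CI 1.07 to 1.54, p = 0.006.

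Neither planned test is significant, yet V3 and V2 clearly differ.

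*Example B: 1,000 per arm, completions 200, 230 and 240.*

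- V2 − V1: OR 1.19, p = 0.103.
- V3 − V1: OR 1.26, p = 0.031.
- V3 − V2: OR = (240/760)/(230/770) = 1.06 (0.86 to 1.30), p = 0.60.

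V3 ranks first and only V3 beats the standard. A reader could take that as evidence for the socks, but the direct comparison shows next to none.

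**Step 4. How often would the planned tests miss a V3 − V2 difference?**

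Simulation of 400,000 trials per setting, Wald tests at two-sided 0.05. The figure is the probability that V3 − V2 is significant while neither planned test is.

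| True rates V1/V2/V3 | Arm sizes | Probability |
|---|---|---|
| 40/37/43% | 500 each | 24% |
| 40/37/43% | 1,000 each | 29% |
| 40/37/43% | 2,000 each | 15% |
| 40/37/43% | 1,500/750/750 | 20% |
| 40/37/43% | 600/1,200/1,200 | 41 to 42% |
| 40/40/46% | 1,000 each | 10.5% |
| 40/42/46% | 1,000 each | 3.9% |
| 40/43/46% | 1,000 each | 1.7% |
| 40/43/49% | 1,000 each | 0.5% |

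The first five rows put V1 midway on purpose. The last three follow the direction of H1a and H1b, and there this kind of miss is uncommon. The misreading in Example B does not depend on V1 lying midway.

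**The case against.** The strongest reply is that the SAP does address the pair. It names V2 and V3 and says there is no hypothesis, which can be read as a deliberate choice to leave the comparison outside the formal tests. The main evaluation in the Introduction is against the standard mailer, and H1a and H1b match that. The heading question can be read to include V2 versus V3, and nothing forbids the contrast. The team can compute it from the fitted model, and a reader can compute it from completions and totals per arm. The 29% figure also needs V2 to do worse than the standard, contrary to H1a.

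Much of this is right, and it limits the point. The gap is in prespecification and reporting; the randomised design is sound and the contrast is estimable. The miss rates depend heavily on the assumed rates. V3 versus V2 also measures a package rather than the socks alone.

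It does not remove the point. Having no predicted direction neither withdraws the aim in the Introduction nor makes an estimate unnecessary, since a two-sided test or interval needs no direction. The plan commits to reporting neither the contrast nor the arm counts. The case for 12 months is weaker, because the gift aim names no time point and 12-month completion is a secondary outcome; an estimate is enough there.

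**Conclusion.** The concern holds and should be fixed. Followed as written, the plan gives the stated gift aim no prespecified analysis and leaves the V2-or-V3 choice without a planned measure of uncertainty. This rests on the documents' text alone: the stated aim, the arm definitions and the V1-reference coding.

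Its numerical size cannot be fixed, because the documents give no rates, sample size or allocation ratio. Under the assumptions shown, the chance that the planned tests are both silent while V3 and V2 differ significantly runs from 0.5% to about 42%. H1a and H1b are unaffected.

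**What to change.** Before the data are examined, add to the Primary Research Question that V3 versus V2 will be estimated as a two-sided contrast (b3 − b2) from the planned logistic model for 6-month mammogram completion, with odds ratio and 95% CI. Do the same for 12-month completion, as an estimate only. Report completions and totals for each arm.

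State that the contrast measures the sock package (socks, envelope, closing line), that it is non-confirmatory, and that a non-significant or wide result does not show that the gift has no effect. Keep H1a and H1b as they are. If the data have been examined by the time this is added, label the contrast as added afterwards.

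The cost is a few lines of SAP text and one linear contrast in each of two models already planned, with no new data. The downside is one more comparison at each time point. If all three 6-month pairwise tests were read as confirmatory at 0.05, the family-wise error when no arms differ would be:

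| Assumed allocation V1:V2:V3 | Two planned tests | All three tests |
|---|---|---|
| 1:1:1 | 9.1% | 12.2% |
| 2:1:1 | 9.5% | 12.1% |
| 1:2:2 | 8.5% | 12.1% |

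That increase is the reason for the non-confirmatory label.
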